**Figure JAIN.6.1. Illustration of graphical multiple testing procedure with initial  $\alpha$  allocation and weights.**

The primary null hypothesis includes testing whether the baricitinib 4-mg + TCS and the baricitinib 2-mg dose + TCS are superior to placebo + TCS at the primary endpoint defined as the proportion of patients achieving EASI75 at Week 16.

Figure JAIN.6.1 depicts the graphical testing scheme (including testing order, interrelationships, Type I error allocation, and the associated propagation).

There will be no adjustment for multiple comparisons for any other analyses.

## 6.5. Patient Disposition

An overview of patient populations will be summarized by treatment group. Frequency counts and percentages of patients excluded prior to randomization by primary reason for exclusion will be provided for patients who failed to meet study entry requirements during screening.

A listing of patient disposition will be provided for all randomized patients, with treatment assignment, the extent of their participation in the study, and the reason for discontinuation.

Patient disposition through Period 2 will be summarized using the ITT population. Frequency counts and percentages of patients who complete the study treatment or discontinue treatment early will also be summarized separately by treatment group for patients who are not rescued and for patients who are rescued, along with the reason for study treatment discontinuation.

Frequency counts and percentages of patients who complete the study treatment visits or discontinue early from the study, along with whether they completed follow-up, will be

summarized overall and separately by treatment group for patients who are not rescued and for patients who are rescued, along with the reason for study discontinuation.

Reasons for discontinuation from the study will be summarized by treatment group and compared between groups using Fisher's exact test.

Patient Treatment Disposition in Period 3 and Period 4 will be summarized using the Long-Term Extension Substudy population, the Long-Term Extension Non-responder population, and the Long-Term Extension responders/partial responders who did not enter the Substudy, respectively. Frequency counts and percentages of patients who complete the study treatment, discontinue treatment early (with discontinuation reasons), or ongoing on-treatment will be summarized by treatment group.

Patient Study Disposition in Period 3 and Period 4 will be summarized using the Long-Term Extension Substudy population, the Long-Term Extension Non-responder population, and the Long-Term Extension responders/partial responders who did not enter the Substudy, respectively. Frequency counts and percentages of patients who complete the study, discontinue study early (with discontinuation reasons), or ongoing will be summarized by treatment group.

## 6.6. Patient Characteristics

Patient characteristics including demographics and baseline characteristics will be summarized descriptively for the **24-week interim analysis** (ITT population), and Final analysis (LTE Substudy Population and LTE Non-responder Populations, and LTE responders/partial responders who did not enter the Substudy).

Historical illnesses and pre-existing conditions will be summarized descriptively for the **24-week interim analysis** (ITT population) by treatment group for the ITT population.

No formal statistical comparisons will be made among treatment groups unless otherwise stated.

### 6.6.1. Demographics

The following demographic information will be categorized and presented as above:

- Age (years)
- Age group (<65 years vs  $\geq$ 65 years)
- Age group (<65 years,  $\geq$ 65 years to <75 years,  $\geq$ 75 years to <85 years,  $\geq$ 85 years)
- Gender (male, female)
- Race (American Indian or Alaska Native, Asian, Black or African American, Native Hawaiian or Other Pacific Islander, White, Multiple)
- Region (Europe [EU], Japan [JP], Rest of World [ROW])
- Country (Austria, Belgium, Finland, France, Germany, Italy, Netherlands, Poland, Spain, Switzerland, UK, Japan, Brazil, Russia)
- Weight (kg)

- Weight group (<60 kg,  $\geq$ 60 kg to <100 kg,  $\geq$ 100 kg)
- Height (cm)
- BMI (kg/m^2)
- BMI group (<25 kg/m^2,  $\geq$ 25 to <30 kg/m^2,  $\geq$ 30 kg/m^2)
- Ethnicity (Hispanic, non-Hispanic)

A listing of patient demographics will also be provided for the ITT population.

### **6.6.2. Baseline Disease Characteristics**

The following baseline disease information will be categorized and presented for baseline AD clinical characteristics, baseline health outcome measures, and other baseline demographic and disease characteristics as described above:

- Duration since AD diagnosis (years)
- Duration since AD diagnosis category (0 to <2 years, 2 years to <5 years, 5 years to <10 years, 10 years to <20 years,  $\geq$ 20 years)
- Age at Diagnosis (years)
- Age Group at Diagnosis (<18 years,  $\geq$ 18 years to <50 years,  $\geq$ 50 years)
- Habits (Alcohol: Never, Current, Former; Tobacco: Never, Current, Former)
- Skin Infections treated with a pharmacological agent within past year (yes, no, unknown; number if yes)
- Atopic Dermatitis Flares within past year (yes, no, unknown; number if yes)
- Validated IGA score
- Eczema Area and Severity Index (EASI) score
- Scoring Atopic Dermatitis (SCORAD)
- Body Surface Area (BSA) affected by AD
- Hospital Anxiety Depression Scale (HADS) subscales
- Patient Oriented Eczema Measure (POEM)
- Itch Numeric Rating Scale (NRS)
- Atopic Dermatitis Sleep Scale (ADSS) Item 2
- Dermatology Life Quality Index (DLQI)
- Skin Pain NRS
- Patient Global Impression of Severity AD (PGI-S-AD)
- Baseline renal function status: impaired (estimated glomerular filtration rate [eGFR] <60 mL/min/1.73 m^2) or not impaired (eGFR  $\geq$ 60 mL/min/1.73 m^2)

- Immunoglobulin E (IgE): intrinsic (<200 kU/I) or extrinsic ( $\geq 200$  kU/I)
- Prior therapy
  - Topical therapy only
  - Systemic therapy only
- Prior phototherapy use
  - Yes, No
  - Yes (type of phototherapy), No
  - If yes, reason for discontinuation of latest phototherapy
- Prior topical calcineurin inhibitor (TCNI) therapy use
  - Yes, No (reason for not using TCNI)
- Prior cyclosporine use (all prior uses, independent of the outcome)
  - Yes, No
- Prior cyclosporine use (cyclosporine ineligible, eligibility criteria)
  - Yes, No

Note: Cyclosporine ineligible (yes, no)

Set to “yes” if the following reasons were selected for either not using the medication or discontinuing the medication:

- Reason for not using the medication: contraindication
- Reason for discontinuation (at least once in case patient took cyclosporine on several occasions): inadequate response, intolerance to medication, or contraindication

All patients in JAIN should be cyclosporine ineligible.

### **6.6.3. Historical Illness and Pre-existing Conditions**

Historical illnesses are defined as those conditions recorded in the Pre-existing Conditions and Medical History electronic case report form (eCRF) or from the Prespecified Medical History: Comorbidities eCRF with an end date prior to the informed consent date. The number and percentage of patients with selected historical diagnoses will be summarized by treatment group using the ITT population. Historical diagnoses will be categorized using the Medical Dictionary for Regulatory Activities (MedDRA®, most current available version) algorithmic standardized MedDRA queries (SMQs) or similar predefined lists of preferred terms (PTs) of interest.

Pre-existing conditions are defined as those conditions recorded in the Pre-existing Conditions and Medical History eCRF, the Prespecified Medical History: Comorbidities eCRF, or the Adverse Events eCRF with a start date prior to the first dose of study treatment and an end date at or after informed consent or ongoing. For events occurring on the day of the first dose of study treatment, the date and time of the onset of the event will both be used to determine if the

event was pre-existing. Conditions with a partial or missing start date (or time if needed) will be assumed to be ‘not pre-existing’ unless there is evidence, through comparison of partial dates, to suggest otherwise. Pre-existing conditions will be categorized using the MedDRA SMQs or similar predefined lists of PTs of interest. Frequency counts and percentages of patients with selected pre-existing conditions will be summarized by treatment group using the ITT population.

## 6.7. Treatment Compliance

**For 24-week interim analysis**, patient compliance with study medication will be assessed for the following:

- Week 0 (Visit 2) through Week 16 (Visit 8) or Early Termination using the ITT population.
- Week 0 (Visit 2) through Week 24 (Visit 10) or Early Termination using the ITT population.

**For 52-week interim analysis**, patient compliance with study medication will be assessed for the following:

- Week 0 (Visit 2) through Week 52 (Visit 14) or Early Termination using the ITT population.

**For 104-week interim analysis**, patient compliance with study medication will be assessed for the following:

- Week 52 (Visit 14) through Week 104 (Visit 22) or Early Termination using the Long-Term Extension Substudy Population, and the Long-Term Extension Non-responder Population.

**For Final analysis**, patient compliance with study medication will be assessed for the following:

- Week 52 (Visit 14) through Week 200 (Visit 28) or Early Termination using the LTE Substudy Population, the LTE Non-responder Population & LTE responders/partial responders who did not enter the Substudy

All patients are expected to take 3 tablets daily from a blister pack as described in the protocol. Each blister pack contains 27 tablets. A patient is considered noncompliant if he or she misses >20% of the prescribed doses during the study, unless the patient’s study drug is withheld by the investigator. For patients who had their treatment temporarily interrupted by the investigator, the period of time that dose was withheld will be taken into account in the compliance calculation.

Compliance in the period of interest up to Visit  $x$  will be calculated as follows:

$$\text{Compliance} = \frac{\text{total number of tablets dispensed} - \text{total number of tablets returned}}{\text{expected number of total tablets}}$$

where

- Total number of tablets dispensed: sum of tablets dispensed in the period of interest prior to Visit  $x$ ;
- Total number of tablets returned: sum of the tablets returned in the period of interest prior to and including Visit  $x$ ;
- Expected number of tablets: number of days in the period of interest\*number of tablets taken per day = [(date of visit – date of first dose + 1) – number of days of temporary drug interruption]\*number of tablets taken per day

A patient will be considered significantly noncompliant if he or she misses more than 20% of the prescribed doses of investigational product during the study, unless the patient's investigational product is withheld by the investigator for safety reasons. Similarly, a patient will be considered significantly noncompliant if he or she is judged by the investigator to have intentionally or repeatedly taken 20% more than the prescribed amount of investigational product during the study. Patients who are significantly noncompliant through Week 16 will be excluded from the PPS population.

Descriptive statistics for percent compliance and noncompliance rate will be summarized for the ITT population by treatment group for Week 0 through Week 16 and Week 0 through Week 24 and Week 0 through 52. Subintervals of interest, such as compliance between visits, may also be presented. The number of expected doses, tablets dispensed, tablets returned, and percent compliance will be listed by patient for Week 0 through Week 16, Week 0 through Week 24, and Week 0 through Week 52. Additionally, treatment compliance will be summarized for the LTE Substudy Population, the LTE Non-responder Population & LTE responders/partial responders who did not enter the Substudy populations from Week 52 through Week 200.

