5.1.2. Period 2: Double-Blind Placebo-Controlled Treatment

At Visit 2 (Week 0, baseline), study eligibility for each patient will be reviewed, based on all inclusion and exclusion criteria (Section 6), and laboratory test results. Patients who meet all criteria will proceed to randomization and begin the 52-week double-blind, placebo-controlled treatment period.

At Visit 2, laboratory samples will be collected and all assessments should be completed before the patient takes the first dose of investigational product. The first dose of investigational product should be administered on-site.

Patients will be randomized at a 1:1:2:1 ratio to 1 of 4 treatment groups (placebo QD, baricitinib 1-mg QD, baricitinib 2-mg QD, or baricitinib 4-mg QD). Patients will also apply background TCS therapy (e.g., triamcinolone 0.1% cream and/or hydrocortisone 2.5% ointment) on active lesions, as described in Section 7.7.2 (Use of Topical Corticosteroids). Use of TCIs and/or crisaborole (where approved) will be permitted as background therapy on areas where application of TCS is considered inappropriate by investigator (e.g., face, neck, skin folds, genital areas; see Section 7.7.1 [Permitted Medications and Procedures]). High- or ultra-high potency TCS (Class I to III; see Appendix 7) and all systemic therapies used for treating AD will not be allowed, unless used as directed as part of rescue therapy (see guidelines in Section 7.7.5 [Rescue Therapy]) and only at the discretion of the investigator. Rescue to baricitinib will not occur during treatment Period 2.

Assessments of disease severity will be performed by the investigator at all study visits including unscheduled and early termination visits (ETVs). On study visit days, patients are requested not to apply emollients nor TCS until after the assessments are completed. Daily diary collection will continue through all 52 weeks of treatment in Period 2 of JAIN.

The primary efficacy endpoint will be at Week 16 (Visit 8). All patients who permanently discontinue investigational product prior to the primary endpoint, including patients rescued with other systemic medications, should remain in the study to complete the schedule of study visits per protocol up to Week 16 (primary endpoint), when they will complete an ETV. If the patient refuses to continue up to Week 16 and wishes to withdraw consent, an ETV should be completed as soon as logistically possible.

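### The SAP 6.7 compliance denominator keeps running after permanent study drug discontinuation, so a fully adherent patient who stops by about Day 90 and attends Week 16 is scored noncompliant and can be dropped from the per-protocol set

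*SAP*

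**What the plan says.** SAP 6.7 defines compliance as tablets dispensed minus tablets returned, divided by expected tablets. The numerator is confined to the reporting period: dispensed tablets are the "sum of tablets dispensed in the period of interest prior to Visit" in question. The denominator begins "Expected number of tablets: number of days in the period of interest\*number of tablets taken per day" and is then written out as a day count, "date of visit – date of first dose + 1) – number of days of temporary drug interruption", multiplied by tablets per day.

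A patient is significantly noncompliant if he or she "misses more than 20% of the prescribed doses of investigational product during the study", with an exemption when the investigator withholds drug for safety reasons. An earlier sentence in the same section gives the exemption without the safety condition. The consequence is stated directly: "Patients who are significantly noncompliant through Week 16 will be excluded from the PPS population".

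On follow-up, Protocol 5.1.2 says that patients who permanently stop drug before the primary endpoint, including those rescued with systemic medication, "should remain in the study to complete the schedule of study visits per protocol up to Week 16", where they have their early termination visit. SAP 6.2.1 also defines the PPS by compliance, but over Period 2 up to Week 52 rather than to Week 16.

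**The concern.** The verbal rule and the formula disagree. The rule concerns prescribed doses, and none are prescribed after permanent discontinuation. The formula still counts every day up to the visit as a dosing day, because it subtracts temporary interruption and nothing else. A patient who followed the prescription exactly, stopped for good, and then attended Week 16 as the protocol asks is therefore charged with missed doses.

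What is at stake is PPS membership and the compliance tables and listings. SAP 6.2.1 repeats the primary and key secondary analyses in the PPS, and Table JAIN.6.8 runs the categorical ones with nonresponder imputation under the primary censoring rule. A patient who stopped drug before Week 16 is a nonresponder at Week 16 in those analyses. Excluding such patients through the compliance score takes out nonresponders only. Some will have stopped for reasons tied to outcome: Protocol 8.1.2 requires permanent discontinuation on systemic rescue.

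A second, smaller point concerns the extension. The numerator is limited to the period, but the first-dose date in the denominator carries no such limit.

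**Working it through.** Neither document states a numeric compliance result, so there is no figure to reproduce. The check applies the written formula to a hypothetical patient who takes every tablet until the last dose and has no temporary interruption.

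**Inputs**
- Day count and numerator: SAP 6.7, as above.
- Tablets per day: 3 ("All patients are expected to take 3 tablets daily from a blister pack"). This cancels in the ratio.
- Cut-off: compliance below 80% (SAP 6.7 and 6.15).
- Week 16 visit: nominal Day 113 (7 × 16 + 1), with the ±4 days of the Schedule of Activities, so Days 109 to 117.
- Nominal Week 52, 104 and 200: Days 365, 729 and 1401.

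**Step 1: permanent stop before Week 16.** With last dose on Day L and visit on Day V, the score is 3L / 3V = L/V. At V = 113:
- Day 28: 28/113 = 24.8%
- Day 56: 56/113 = 49.6%
- Day 60: 60/113 = 53.1%
- Day 84: 84/113 = 74.3%
- Day 90: 90/113 = 79.6% (fails)
- Day 91: 91/113 = 80.5% (passes)

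The last failing day is Day 87 for a visit on Day 109 (87/109 = 79.8%) and Day 93 for a visit on Day 117 (93/117 = 79.5%). A completer scores 112/113 to 113/113, or 99% to 100%, and is not affected. If the count ended at discontinuation, every one of these patients would score L/L = 100%.

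**Step 2: what exclusion does to PPS response rates.** The documents give no early-discontinuation rate. As an assumption, take 5 to 10 such patients per 100 in an arm, all nonresponders by imputation. With the planning rates of SAP 6.1 (20% on placebo, and 20% + 25% = 45% on active):
- Active: 45/95 = 47.4% to 45/90 = 50.0%
- Placebo: 20/95 = 21.1% to 20/90 = 22.2%
- Difference, planned at 25 points: 25/95 = 26.3 or 25/90 = 27.8 points if removals are equal. It is 45/95 − 20/90 = 25.1 or 45/90 − 20/95 = 28.9 points if they are unequal.

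These figures show the mechanism. They do not estimate its size in this trial.

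**Step 3: extension.** A perfect taker from Day 365 has 729 − 365 + 1 = 365 dosing days by Week 104 and 1401 − 365 + 1 = 1037 by Week 200.
- First dose read as Week 0: 365/729 = 50.1% and 1037/1401 = 74.0%. The score (V − 364)/V does not reach 80% until Day 1820 (Week 260), beyond the end of the study.
- First dose read as first in the period: 365/365 and 1037/1037, both 100%.

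**The case against.** Four points can be made against this.

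*Some of these patients are protected.* The exemption for drug withheld on safety grounds plausibly covers many adverse-event stops. The assessment window also closes at early termination. Protocol 7.7.5.1 sends patients needing systemic rescue to that visit before the new treatment starts, and Protocol 5.1.2 gives patients who refuse to continue an early visit. Their scores are little affected. This stands, and a reader who inferred that every permanent stop before Day 90 fails the cut would go too far. It does not remove the problem: Protocol 5.1.2 places the early termination visit at Week 16 for those who stay, systemic rescue included, and Protocol 7.7.5.1 itself encourages visits through Visit 8. The exemption's wording does not reach systemic rescue or a patient's own decision to stop.

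*Excluding early discontinuers may be intended.* Leaving out patients who did not receive most of the treatment is a common per-protocol choice, and SAP 6.15 defers exclusion categories to a Trial Issue Management Plan that is not among these documents. That may be so. If it is, it belongs in a criterion of its own, since the compliance rule as worded concerns prescribed doses.

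*The extension reading is uncharitable.* The same line calls the count the days in the period, and SAP 6.2.2.1 anchors the Week 52 baseline on the first Period 3 dose. This stands: it is a missing qualifier, not a demonstrated error. In its favour as a point worth fixing, SAP 6.2.1 names the Period 3 first dose explicitly where it is meant.

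*The impact is limited.* The PPS supports sensitivity analyses only. This stands too.

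**Conclusion.** The formula as written gives wrong compliance values for patients who permanently stop drug, took all tablets until then, and are followed to Week 16. With a visit on Day 113 they fall below 80% if the last dose is on or before Day 90 (Day 87 to Day 93 across the visit window). Unless the safety exemption applies, SAP 6.7 excludes them from the PPS. In the categorical PPS analyses that removes nonresponders, in part for reasons related to outcome. The result rests on the literal formula; the programmed derivation cannot be seen.

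The reach is the PPS sensitivity analyses and the compliance summaries and listings. The primary ITT analysis with nonresponder imputation is not affected. The number of patients involved cannot be computed, and nothing in the documents shows that it differs by arm, although a reader might infer this.

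A reader might also infer that the extension formula removes patients from the PPS or halves extension compliance. The documents do not support the first: PPS membership depends on Period 2 alone (SAP 6.2.1, 6.7 and 6.15). The second follows only if the first dose is taken to be the Week 0 dose, and even then the score at Week 200 is 74%. Descriptive extension summaries alone would be distorted.

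This should be corrected. It is not critical to the trial's main conclusion.

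**What to change.** Replace the day count in SAP 6.7 with:

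expected days = min(visit date, documented date of permanent study drug discontinuation) − date of first dose in the period of interest + 1 − days of temporary interruption.

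The cut-off should be the documented discontinuation date and not the last dose taken. Ending at the last dose would give 100% to a patient who simply stopped taking tablets without being discontinued, which is the behaviour the measure is meant to detect.

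If early discontinuers are meant to be left out of the PPS, state that as a separate criterion. Align the PPS compliance window, which is Week 52 in SAP 6.2.1 and Week 16 in SAP 6.7.

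The cost is one formula line, a sentence or two on the PPS, and reprogramming one derived variable. SAP 6.16 reports the 24-week analysis as already conducted, so for that analysis the step is to check the derivation as programmed and to correct or document any difference.

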## 6.8. Background Therapy

Throughout the study, background TCS therapy (for example, triamcinolone 0.1% cream and/or hydrocortisone 2.5% ointment) are to be used on active lesions (see JAIN protocol Section 7.7.2).

- Mean number of days without use of background TCS over 16 weeks and 52 weeks

The following analyses will be performed: The total number of days that the patients did not use background TCS will be summarized by both potencies throughout the entire 16-week treatment period and 24-week treatment period for 24-week interim analysis, and the entire 52-week treatment period for 52-week interim analysis. For 24-week interim analysis, the main analysis applies censoring rule #1. After patients who are rescued or discontinue investigational products, it is assumed that background TCS would be applied each day. In case of missing values in the daily diary, it will be assumed that background TCS has been used. Analysis will be done for Week 16 via ANOVA, with geographic region, baseline disease severity, and treatment as factors in the model. A secondary analysis will apply censoring rule #2, with the same assumptions for missing values as described above. For 52-week interim analysis, analysis will be done via ANOVA, with geographic region, baseline disease severity, and treatment as factors in the model.

- Mean number of days without use of background TCS in Period 3/4

Mean of the number of days that the patients did **not** use background TCS will be summarized for Long-Term Extension Period 3 (Week 52 through Week 68). Only descriptive statistics will be provided without using the censoring rule.

- Mean gram quantity of background TCS used over 16 weeks and 52 weeks, Week 52 through Week 104 (tube weights)

Descriptive statistics for drug accountability of topical low and moderate potency background medication provided by the sponsor will be presented, including the amount utilized throughout the 16-week and 24-week treatment period for 24-week interim analysis, and the entire 52-week treatment period for 52-week interim analysis. The total amount in grams for low and moderate potency, as well as the sum of both potencies will be summarized between visits. If a returned tube is not weighed in grams, the tube can be classified as partially used, fully used, unused, or unknown. Partially used background medication tubes will be considered to be 50% used, whereas fully used and unused will be considered as 100% and 0% used, respectively. When drug accountability is not performed for a particular tube of background medication or an answer of unknown is given for a tube which is not returned, that particular tube will not be included in the analysis.

For 24-week interim analysis, the main analysis on the total amount of background TCS throughout the entire 16-week treatment period will apply censoring rule #1. After patients who get rescued or discontinue investigational product, whichever is earlier, it is assumed that they would use the same amount of TCS as they did before. Analysis will be done via analysis of variance (ANOVA), with geographic region, baseline disease severity, and treatment as factors in the model. The secondary analysis will apply censoring rule #2 with the same assumptions as described above. For 52-week interim analysis, analysis will be done via ANOVA, with geographic region, baseline disease severity, and treatment as factors in the model.

- Mean gram quantity of background TCS used in Period 3 (tube weights)

For Long-Term Extension Period 3 (Week 52 through Week 104), the total amount utilized in grams for low and moderate potency will be summarized between visits (Week 52 through Week 56, Week 56 through Week 60, Week 60 through Week 64, and so on) as well as throughout the treatment period from Week 52 through 104 (Period 3). The total amount utilized will also be presented for the aforementioned visit intervals, irrespective of potency. Only descriptive statistics will be presented. No ANOVA model will be implemented. No censoring rule will be applied.

Note: As rescue TCS (high/ultra-high potency) is not weighed, an analysis similar to the main analysis described above for the number of days without background TCS cannot be performed. Whether any background TCS is used for each patient is also collected in the diary device each day starting from the first dose date throughout the study.

